### **5.3.1.2 Secondary Endpoints**

#### **(1) Time to Completion of Wound Bed Preparation (unit: day)**

**Define:** duration from the randomization until target wound ready for closure by secondary intervention judged by investigator.

**Evaluation time point:** Day of Randomization (Day 0) and End of Treatment Visit

**Measurement:** the date deemed ready for closure by secondary intervention - the date of the randomization + 1.

**Statistical method:** the difference between investigational group and control group will be assessed.

#### **(2) Wound Area Reduction Rate (unit: %)**

**Define:** wound area change over 14 days or until deemed ready for closure by investigator (whichever occurred first).

**Formula:** wound area reduction rate = (wound area before study treatment –wound area after study treatment 14 days or deemed ready for closure before 14 days) ÷ wound area before study treatment×100%.

**Measurement:** 3D Wound Imaging System, the value for area can be collected from the 3D wound imaging system report directly.

**Evaluation time point:** Day of Randomization (Day 0), Dressing Change Visit (s), and End of Treatment Visit

**Statistical method:** the difference between investigational group and control group will be assessed.

#### **(3) Wound Clinical Assessments**

**Define:** Wound depth, edges, necrotic tissue type and amount, granulation tissue, undermining, exudate type and exudate amount of target wound after therapy will be evaluated.

**Measurement:** Wound depth, edges, necrotic tissue type and amount, granulation tissue, undermining, exudate type and exudate amount will be evaluated according to

table below.

Wound Depth	1 = non-blanchable erythema on intact skin 2 = Partial thickness skin loss involving epidermis and/or dermis 3 = Full thickness skin loss involving damage or necrosis of subcutaneous tissue; may extend down to but not through underlying fascia; and/or mixed partial and full thickness and/or tissue layers obscured by granulation tissue 4 = Obscured by necrosis 5 = Full thickness skin loss with extensive destruction, tissue necrosis or damage to muscle, bone or supporting structures	
Edges	1 = Indistinct, diffuse, none clearly visible 2 = Distinct, outline clearly visible, attached, even with wound base 3 = Well-defined, not attached to wound base 4 = Well-defined, not attached to base, rolled under, thickened 5 = Well-defined, fibrotic, scarred or hyperkeratotic	
Necrotic tissue type	1 = None visible 2 = White/grey non-viable tissue and/or non-adherent yellow slough 3 = Loosely adherent yellow slough 4 = Adherent, soft, black eschar 5 = Firmly adherent, hard, black eschar	
Necrotic tissue amount	1 = None visible 2 = < 25% of wound bed covered 3 = 25% to 50% of wound covered 4 = > 50% and < 75% of wound covered 5 = 75% to 100% of wound covered	
Granulation Tissue	% change in granulation tissue from baseline utilizing 3D Wound Imaging System and clinical judgement	1 = Skin intact or partial thickness wound 2 = Bright, beefy red; 75% to 100% of wound filled and/or tissue overgrowth 3 = Bright, beefy red; < 75% and > 25% of wound filled 4 = Pink, and/or dull, dusky red and/or fills ~ 25% of wound 5 = No granulation tissue present
Undermining	1 = None present 2 = Undermining < 2 cm in any area 3 = Undermining 2-4 cm involving ≤ 50% wound margins 4 = Undermining 2-4 cm involving > 50% wound margins 5 = Undermining > 4 cm or Tunneling in any area	
Exudate type	1 = None	

	2 = Bloody 3 = Serosanguinous: thin, watery, pale red/pink 4 = Serous: thin, watery, clear 5 = Purulent: thin or thick, opaque, tan/yellow, with or without odor
Exudate amount	1 = None, dry wound 2 = Scant, wound moist but no observable exudate 3 = Small 4 = Moderate 5 = Large

**Evaluation time point:** Day of Randomization (Day 0), Dressing Change Visit (s), End of Treatment Visit.

**Statistical method:** the difference between investigational group and control group will be assessed.

### 5.3.2 Evaluation of Safety

#### (1) Incidence of AEs (unit: %)

**Define:** an AE is any untoward medical occurrence in the course of a trial, whether or not related to the investigational device.

**Evaluation:** type, incidence, seriousness and relatedness of AEs/Adverse device effects (ADEs), and laboratory abnormalities will be reported.

**Formula:** incidence of AEs/ADEs = sum of subject who occurred AEs/ADs ÷ sum of subjects for each group × 100%.

**Statistical method:** the difference between investigational group and control group will be assessed.

**Note:** especially focus on the systemic reactions and local skin/tissue irritation (such conditions as wound secretions and swelling, pain, and local skin color change, etc.)

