#### **5.2.5 Expected Duration of Each Subject's Participation**

The participation duration of each subject is defined as the duration from the time of subject to be enrolled in the trial to the last visit. For each subject, it is estimated that the screening duration is up to 3 days, anticipated treatment i.e. wound bed preparation duration is up to 14 days. In total, expected duration of each subject's participation is up to 17 days. During the period, all patients will have the initial dressing placement and a minimum of 2 dressing changes.

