## **9.2 Analysis of Possibility of Failure**

The non-compliance of trial conduct with protocol, operating procedures not been followed strictly, incomplete records of observations and laboratory results during the clinical trial or lack of source data supporting may cause the failure of this trial, but these factors are controllable.

The physicians who have rich experience for clinical trial will be designated as the investigators. The investigators will be trained about the knowledge of device and operating procedures before the trial to ensure the skillfulness of the operators. Each subject participating in the clinical trial will be followed up comprehensively after procedures. The additional supervision may improve the probability of early detection of any AE. The medical records of each subject will be monitored to observe the occurrence of complications closely and create detailed emergency treatment regimen. In summary, the possibility of failure of clinical trial is small, but also related to the systemic risk operation and the conditions of subjects.

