### 12.1.5 Anticipated AE

Anticipated AEs with NPWT Therapy/Dressing for this trial are summarized in following table.

Skin and Subcutaneous Tissue Reaction/Allergy	Desiccation/injury Skin rash, irritation, blistering Pruritus/itching Skin excoriation/breakdown Skin stripping Skin scarring if significant skin irritation were to occur Maceration Skin hyper/hypo-pigmentation at and/or around dressing application area Erythema/redness, edema, inflammation, or swelling at and/or around dressing application area
Mild Pain or Discomfort	Tenderness/minor ache at and/or around dressing application area Perspiration associated with wearing dressing Auditory irritation (due to mild buzzing sound of negative pressure unit) Decreased sleep or sleep quality Paresthesia (numbness, tingling, prickling, creeping sensation)
Other	Bleeding Cardiac compromise (vagal response, bradycardia) Pulmonary compromise Accidental instillation in a body cavity Localized infection Autonomic dysreflexia (in subjects with spinal cord injury) Retained foreign debris (e.g. foam) in the wound Impairment of mobility/activity (limitation secondary to weight and attachment of therapy unit) Possible tubing entanglement/trip or slip hazard leading to fracture, tissue damage Incorrect therapy unit settings resulting in incorrect frequency/dosing Tunneling Stalled healing/non-progression of healing Deterioration of the wound Systemic reaction (due to allergic reaction to dressing materials)

	Burn secondary to therapy unit or power cord malfunction
--	--

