17.1. INCIDENCE OF AEs (UNIT: %)

Define: an AE is any untoward medical occurrence in the course of a trial, whether or not related to the investigational device.

Evaluation: type, incidence, seriousness and relatedness of AEs/Adverse device effects (ADEs), and laboratory abnormalities will be reported.

Formula: incidence of AEs/ADEs = sum of subject who occurred AEs/ADs ÷sum of subjects for each group×100%.

Statistical method: The incidence of AEs will be summarized by frequency counts along with associated percentages .The Chi square (or Fisher's exact) test will be performed.

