17.3. INCIDENCE OF DEVICE DEFICIENCIES RESULTING IN AE OR SAE (UNIT: %)

Define: see relevant subsections of protocol 13.3.1.

Formula: incidence of Device deficiencies resulting in AE or SAE = sum of subjects experienced device deficiency resulting in AE or SAE ÷sum of subjects for each group×100%.

Statistical method: The incidence of Device deficiencies resulting in AE or SAE will be summarized by frequency counts along with associated percentages. The Chi square (or Fisher's exact) test will be performed, P-values will be reported.

18. Safety Outcomes

All outputs for safety outcomes will be based on safety set.

There will be no statistical comparison for safety variables of this study.

Listings will include scheduled, unscheduled, retest and early discontinuation data.

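### AE and SAE incidence is compared as crude percentages although each subject's observation ends when the wound is judged ready; exposure-adjusted rates should stand beside them

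*Protocol*

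**What the plan says.** **Measure.** Protocol 5.3.2 (1) sets the numerator as the "sum of subject who occurred AEs/ADs", over the subjects in each group, and adds that "the difference between investigational group and control group will be assessed". Item (2) does the same for SAEs and SADEs. SAP 17.1 keeps the denominator, "sum of subjects for each group×100"%, and states that a chi-square or Fisher "test will be performed"; SAP 17.2 repeats this for SAEs. Comparing AE and SAE incidence is a secondary objective (Protocol 4.2, SAP 3.2).

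**Observation time.** The schedule of activities (Protocol 5.5.1) has AE review at screening, Day 0, dressing changes and the end-of-treatment or withdrawal visit, and in no later column. The end-of-treatment visit falls when the investigator deems the wound ready, or at Day 14 ± 1. Protocol 5.2.5 defines participation as "the duration from the time of subject to be enrolled in the trial to the last visit", at most 17 days. The trial is open-label (5.1.2.4).

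**Whether safety is tested.** Against the tests in SAP 17.1-17.3, SAP 18 says: "There will be no statistical comparison for safety variables of this study".

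**After treatment.** Protocol 9.2 states: "Each subject participating in the clinical trial will be followed up comprehensively after procedures". Protocol 12.1.5 lists among anticipated events "Retained foreign debris (e.g. foam) in the wound", localized infection and deterioration of the wound.

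**The concern.** How long a subject is watched for adverse events depends on an efficacy outcome. A wound judged ready on Day 5 contributes about 5 days of observation, and one that is never ready contributes about 14. Both count as one subject in the denominator. If readiness comes sooner in one arm, that arm has less time in which to record an event and its percentage is lower at the same daily risk. A true difference in risk can be exaggerated or hidden in the same way.

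The plan recognises unequal duration elsewhere. SAP 15.2.2 censors subjects in the time-to-preparation analysis, and SAP 15.4 summarises and tests treatment days by arm. Neither is carried into the AE comparison, which has no rate per day, no time-to-event analysis and no fixed period. What is at stake is the interpretation of a stated safety comparison in a registration trial; the primary endpoint is unaffected.

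**Working it through.** **The plan's own figures.** The documents give no expected AE rate and no expected duration by arm for this trial, so there is no safety calculation to reproduce. Maximum participation does reproduce: 3 screening days + 14 treatment days = 17, which leaves no scheduled time after treatment.

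**Inputs**
- Durations, cited: mean 6.8 days (instillation) vs 6.3 days (NPWT) to readiness, from the post-marketing study in Protocol 3.1.3.1, the only durations by therapy in the documents.
- Durations, assumed: 6 vs 10 days, to show a marked difference.
- Daily AE risk, assumed: 1%, 3% or 5%, constant and identical in both arms.
- Subjects: 85 per arm, the maximum in Protocol 6.1.1.

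**Formula.** P(at least one AE) = 1 − exp(−h × days), with every subject in an arm given that arm's mean duration.

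At h = 0.03:
- 6.8 days: 1 − exp(−0.204) = 18.45%
- 6.3 days: 1 − exp(−0.189) = 17.22%; difference 1.23, so 1.2 points (subtracting the rounded 18.5 and 17.2 would give 1.3)
- 6 days: 1 − exp(−0.18) = 16.5%
- 10 days: 1 − exp(−0.30) = 25.9%; difference 9.4 points

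| Daily risk | 6.8 vs 6.3 days | Gap (points) | 6 vs 10 days | Gap (points) |
|---|---|---|---|---|
| 1% | 6.6% vs 6.1% | 0.5 | 5.8% vs 9.5% | 3.7 |
| 3% | 18.5% vs 17.2% | 1.2 | 16.5% vs 25.9% | 9.4 |
| 5% | 28.8% vs 27.0% | 1.8 | 25.9% vs 39.3% | 13.4 |

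The gaps are taken before rounding. In every row the rate per treatment day is the same in both arms, a true rate ratio of 1.0.

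**Effect on the test in SAP 17.1.** The chance that a two-sided 5% test is significant in the direction of the false gap is approximately Φ[(d − 1.96 × SE0)/SE1]. Here d is the gap, SE0 the pooled and SE1 the unpooled standard error, at 85 per arm. The nominal value for one tail is 2.5%.
- 6.8 vs 6.3 days: 3.3%, 4.0% and 4.5% at daily risks of 1%, 3% and 5%.
- 6 vs 10 days: 14.5%, 32.4% and 46.3%.

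The distortion is therefore slight if durations are as close as in the cited study, and serious if they are not.

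**Order of steps at the last visit (Protocol 5.5.2.4).** Dressing removal is item 4, imaging item 5, AE collection item 7 and device deficiencies item 8. Whatever is visible at removal can be recorded. What is not sought is anything that first appears after the visit. Protocol 12.1.6 follows events already identified until they resolve or stabilise, but sets up no search for new ones.

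**The case against.** **Crude incidence is a legitimate quantity.** If treatment ends sooner, fewer events over the course may be a real consequence of the strategy. If skin reactions cluster in the first days, crude incidence depends less on duration, and a constant-rate adjustment could over-correct. This stands. It is a reason to report both measures, not to leave one out.

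**Exposure is not wholly ignored.** SAP 15.4 compares treatment days, SAP 7.1 assigns a study day to events, and SAP 7.2 classes AEs from first application onward as post-baseline. That is true, but nothing joins these data to the AE comparison.

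**No test may be run.** SAP 18 can be read that way. SAP 17.1-17.3 say the opposite, and unadjusted percentages side by side invite the same reading without a p-value.

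Four stronger readings are tempting, and the documents do not support them:
- *The investigational device will look safer.* The cited durations point slightly the other way, and that study found no significant difference (p = 0.7105). It also does not settle the durations here, where the control is a different dressing on wall suction.
- *Events seen at dressing removal are missed.* Removal precedes AE collection at the same visit.
- *Late events are missed mainly in the faster arm.* No post-removal surveillance is scheduled for any subject in either arm. That is a loss of sensitivity, not a differential bias.
- *Protocol 9.2 promises a follow-up visit that was left out.* The sentence is general risk-benefit wording and does not define the procedures meant. It needs reconciling with the schedule, no more.

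**Conclusion.** The concern holds in a limited form. Observation for AEs ends at a visit whose date depends on readiness as judged by an unblinded investigator, while the compared incidences take no account of days observed. Unequal durations would then appear as a safety difference.

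The direction and size are unknown. At an assumed 3% per day the false gap is about 1.2 points, against the instillation therapy, with the only durations cited, and 9.4 points with an assumed 6 vs 10 days. Both figures rest on a constant risk, equal in the two arms, and on mean durations standing in for individual ones; the 9.4 has no support in the documents beyond illustration. The missing search for events after the last visit is a separate, non-differential limitation. The remedy is nearly free and should be adopted before database lock.

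**What to change.** 1. **SAP 17.1 and 17.2.** Beside the crude percentages for AEs, ADEs, SAEs and SADEs, report by arm:
   - first events per 100 treatment days, with days counted from first application to the first event or, if none, to end of treatment or withdrawal;
   - all events per 100 treatment days, with a variance that allows for repeat events within a subject;
   - 95% confidence intervals for both, and the rate difference or ratio between arms.

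   Count events that begin on or after first application, in line with SAP 7.2. State that the between-arm safety interpretation rests on the crude and the adjusted figures together.
2. **SAP 17.1-17.3 and 18.** Reconcile them: either the tests stay and the sentence in SAP 18 goes, or the reverse. Align the result with Protocol 5.3.2.
3. **Protocol 5.5 and 9.2.** State explicitly when collection of new AEs ends, and reconcile the 9.2 sentence with the visit schedule. Report the absence of later surveillance as a limitation.

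**Cost.** Items 1 and 2 are SAP text and programming, using first-application, event and end-of-treatment dates already collected. Item 3 is a clarifying line in an amendment.

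A common AE window to Day 14 (+1) for everyone is not recommended. It would bring in events from closure procedures and institutional care after study treatment, mainly among early finishers. It would give Day-14 finishers almost no time after removal. It could also reach 3 + 15 = 18 days, beyond the 17 stated in Protocol 5.2.5.

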18.1.1. All Adverse Events

The following AE summaries will be described frequency and percentage by treatment group and overall in an overview summary table:

- AEs
- Severity of AE (mild, moderate, severe)
- Serious AEs
- deaths
- Adverse Device Effect
- Serious Adverse Device Effect
- AEs leading to study termination

If a subject experienced more than one adverse event, the AE with the worst severity will be used in the corresponding summaries.

In addition, all AEs will be listed and presented by System Organ Class (SOC) and Preferred Term (PT) and also broken down further by maximum severity of event. If a subject reports an AE more than once within that SOC/ PT, the AE with the worst severity will be used in the corresponding severity summaries.

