18.1.3. The Most Common ($\geq 5\%$ Incidence) Adverse Events

The most common($\geq 5\%$ incidence) adverse events will be listed and presented by SOC, PT and severity.

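### The protocol singles out local skin/tissue irritation and systemic reactions as the focus of AE evaluation, but the SAP text analyses neither as a group and gives no between-arm estimate for them

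*Protocol*

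**What the plan says.** **Protocol.** Section 5.3.2, under incidence of AEs, states that "the difference between investigational group and control group will be assessed" and adds a note to "especially focus on the systemic reactions and local skin/tissue irritation (such conditions as wound secretions and swelling, pain, and local skin color change, etc". Section 12.1.5 lists anticipated AEs under three headings. The first is "Skin and Subcutaneous Tissue Reaction/Allergy", the second covers mild pain or discomfort, and the third is a mixed group that includes a systemic allergic reaction.

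**SAP.** Section 17.1 repeats the definition, evaluation line and formula from protocol 5.3.2 and leaves out the note. For analysis it says "The incidence of AEs will be summarized by frequency counts along with associated percentages" and "The Chi square (or Fisher's exact) test will be performed". Section 18.1.1 says "all AEs will be listed and presented by System Organ Class (SOC) and Preferred Term (PT"), with a further breakdown by maximum severity. Section 18.1.3 adds a table for events at 5% or more: these "adverse events will be listed and presented by SOC, PT and severity". Section 18.1.5 tabulates ADEs by SOC, preferred term and severity. Section 18 opens with "There will be no statistical comparison for safety variables of this study". Section 2 declares no change from the protocol's planned analyses.

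**The concern.** The protocol tells the reader which harms matter most, and the analysis plan never forms those categories. The outputs it does plan sit on either side of them. The any-AE incidence is broader and mixes in events that have nothing to do with the dressing. SOC and preferred-term rows are narrower, or cut along other lines: swelling, pain, secretions and colour change belong together in the protocol's note, but protocol 12.1.5 already spreads local events over more than one heading, and coding may spread them over more than one SOC.

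At stake is whether the report can state by how much the arms differ in local reactions around the dressing. That matters because saline instillation is given in one arm only (protocol 5.4.1 and 5.4.2), and because the device precautions in protocol 3.3.3 warn of maceration and of sensitivity to drape and foam. SAP 5.1 provides for no DMC, so the final tables carry the safety comparison. A grouping chosen after the data are seen would be open to challenge.

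**Working it through.** **Step 1. Is there a planned figure to reproduce?** Not for safety: the documents give no AE rate, sample size or power for any safety outcome. The only sizing is for the primary endpoint. With margin 20%, SD 40% and one-sided 0.025, the noncentral t gives power 0.801 at 64 per arm, matching the stated 80% for 128 evaluable subjects. For safety I take 85 per arm, half of the 170 maximum in protocol 6.1.1.

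**Step 2. What each planned output covers.**

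| SAP output | What it gives | What it leaves out |
|---|---|---|
| 17.1 any AE/ADE, chi-square or Fisher | Incidence per arm | Not specific to the named categories |
| 18.1.1 AEs by SOC and preferred term | Counts per arm, all terms | No row that unites the local reactions or is limited to the target wound |
| 18.1.3 events at 5% or more | Supplement to 18.1.1 | Rarer terms, though these remain in 18.1.1 |
| 18.1.5 ADEs by SOC, preferred term, severity | Related events only | No grouping; depends on investigator causality in an open-label trial |
| 15.2.4 exudate type and amount, Wilcoxon | Between-arm comparison of secretions | Swelling, pain, skin colour |
| 18.4 physical examination | Summary by visit and arm | No between-arm estimate specified |

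**Step 3. Illustration of size (all rates assumed).** Six local-reaction terms, independent, each 3% with the device and 1% with control; two-sided 0.05 as in SAP 7.5; Fisher power by exact enumeration.

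- Any local reaction, device: 1 − (1 − 0.03)^6 = 0.1670. Control: 1 − (1 − 0.01)^6 = 0.0585. Difference: 0.1085.
- Grouped incidence, 85 per arm: power 0.545. At 70 per arm: 0.44.
- Any-AE test with a proportion b of subjects having other AEs: rate = 1 − (1 − b)(1 − p), where p is the grouped rate.

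| b | Device | Control | Fisher power |
|---|---|---|---|
| 20% | 33.4% | 24.7% | 0.19 |
| 40% | 50.0% | 43.5% | 0.11 |
| 60% | 66.7% | 62.3% | 0.07 |

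- One single term, 3% against 1%: power 0.020. This is only a yardstick, since the SAP plans no test by term.
- 5% table: a given term reaches 5 of 85 in the device arm with probability 0.1125. At least one of six does so with probability 1 − (1 − 0.1125)^6 = 0.51.

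**Step 4. A second assumed scenario.** Grouped rate 10% against 25%, 85 per arm: Fisher power 0.68 grouped. Split evenly over two SOCs, 0.38 per SOC; over three, 0.22; over five terms, 0.09 per term. In the any-AE test it is 0.32, 0.18 and 0.10 with 20%, 40% and 60% background. The ordering is the same.

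**Step 5. What an estimate would look like.** In the step 3 scenario the standard error of the risk difference is √(0.1670 × 0.8330/85 + 0.0585 × 0.9415/85) = 0.048. A typical 95% CI is then 10.9 ± 9.4 percentage points, about 1.5 to 20.2. That is wide but informative, and no planned output provides it.

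**The case against.** A reader might infer that the SAP has no analysis of these harms at all, or reduces them to single preferred terms, so that a real excess would go unseen. The documents do not support that. SOC is itself a grouping. To the extent that the skin reactions code to one SOC, that row gives a per-arm subject count close to what is wanted, and over two or three SOCs the loss is partial (step 4). ADE tables restrict to related events and count missing relatedness as related, which reduces dilution. The 5% table adds to the full tables and hides nothing. Secretions are compared between arms through the exudate scores, and the physical examination is summarised by arm at each visit.

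It can also be said that the protocol sentence is a note directing attention, and that the promise to assess a difference attaches to AE incidence, which 17.1 tests. That is a fair reading, so this is a gap in the analysis of a named focus rather than a broken commitment. The power figures rest on invented rates, and even the grouped test misses the assumed excess in about 45% of trials.

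Finally, SAP Section 8 gives the output templates priority over the text. They are not among the documents, so a grouped table there cannot be ruled out.

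What survives is narrower: nothing in the SAP text yields a subject-level incidence, or a between-arm estimate, for either named category.

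**Conclusion.** The point holds as a gap in grouping and estimation, not as an absence of safety analysis. The SAP text drops the protocol's stated focus and leaves it to be pieced together from an any-AE test, SOC and preferred-term tables, ADE tables, exudate scores and examination summaries. An excess spread over several terms and SOCs is harder to see there: about 0.55 power grouped against 0.19 to 0.07 in the any-AE test. Those figures depend wholly on assumed rates, independent terms and 85 per arm. The ordering also holds in the second scenario; the sizes are not predictions.

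The position is weakened further because SAP 18 rules out statistical comparison of safety variables while 17.1 to 17.3 specify tests, so even the any-AE comparison is in doubt. The improvement is worth making because it is cheap and uses data already collected.

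**What to change.** Before database lock:

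1. Fix a medically reviewed term list for two groups: (a) local skin/tissue reaction at or around the target-wound dressing, and (b) systemic reaction. Start from protocol 12.1.5 and 5.3.2. The 12.1.5 headings cannot be used unchanged: local events cross them, and the pain group includes items such as auditory irritation and poor sleep that should be left out.
2. Add one Safety Set table by arm to SAP 17.1: subjects with at least one event in each group, percentage, and risk difference with 95% CI. Present it as estimation, not as a powered test.
3. Reconcile SAP 17.1 to 17.3 with the opening statement of SAP 18, so that it is clear which safety comparisons will be made. Otherwise the new table inherits the conflict.
4. If the output templates already contain such a table, put its term list in the SAP text.

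The cost is a short medical review of the term list and one extra table. No new data are needed.
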